| 12.1. Appendix 1 - Abbreviations and Trademarks | 58 |
| 12.2. Appendix 2 –Dermal Response Score | 59 |
| 12.3. Appendix 3 - Fitzpatrick Skin Type Grading | 61 |

| Document Name | \$\$\text{sice}(7\text{P85}\text{typerot}(2\text{Q})7\text{75} | | | | | | | | |
|----------------------|--|---------------------|----------------------|--|--|--|--|--|--|
| Туре | Version | Document Identifier | Effective Date | | | | | | |
| eldo climitralleatoc | 0.0; CURRENT; Most-Recent; Registived | 090032d580e42556 | 31-Jan-2017 14:20:06 | | | | | | |
| Reason For Issue | Auto Issue | | | | | | | | |

PROCESS FOR AMENDING THE PROTOCOL

Protocol modifications to ongoing studies which could potentially adversely affect the safety of subjects or which alter the scope of the investigation, the scientific quality of the study, the experimental design, dosages, duration of therapy, assessment variables, the number of subjects treated, or subject selection criteria are considered major/substantial amendments and must be made only after appropriate consultation between an appropriate representative of GSKCH and the investigator.

Details of amendments to the protocols should be recorded on the following page. Protocol modifications must be prepared by a representative of GSKCH. All changes must be justified in the Reason for Amendment section of the following Protocol Amendment Page. Approval of amendments will be made by the original protocol signatories or their appropriate designees.

All major/substantial protocol modifications must be reviewed and approved by the appropriate IRB in accordance with local requirements, before the revised edition can be implemented.

All non-substantial/minor/administrative amendments should be submitted to the IRB as per country specific requirements. In some countries pre-approval of a minor amendment is not required and will just be held on file by the sponsor and investigator.

| Document Name | siki/2017985kggrot/20271585 | | | | | | | | |
|---------------------|--|---------------------|----------------------|--|--|--|--|--|--|
| Туре | Version | Document Identifier | Effective Date | | | | | | |
| eldo chimitrelletto | 0.0: CURRENT: Most-Recent: Rffigiretiwed | 090032d580e4@4%6 | R1-Jan-2017 14:20:06 | | | | | | |
| Reason For Issue | Auto Issue | | | | | | | | |

PROTOCOL AMENDMENT PAGE

Details of all amendments should be recorded in the table below. Affected sections should be listed in the table; the actual amendment/ change should be made in the relevant section of the main protocol.

To highlight the change, the following features will be used:

To add text: Use of **CAPITAL LETTERS, BOLD AND UNDERLINE**

To delete text: Use of Strikethrough e.g. strikethrough

| Amendment No. & New Protocol | Type of Amendment | Reason for Amendment | Other Documents Requiring | Section(s) Amended | PI Amendment Agreement Signature & |
|------------------------------------|-----------------------|----------------------|------------------------------------|--------------------|--|
| Version No. | | | Amendment | | Date |
| Amendment No.: | Non-Substantial/Minor | | Informed Consent Yes No | | Signature: |
| Protocol Version No.: | Substantial/ Major | | Safety Statement Yes No CRF Yes No | | Date: |
| Amendment No.: | Non-Substantial/Minor | | Informed Consent Yes No | | Signature: |
| Protocol Version No.: | Substantial/ Major | | Safety Statement Yes No CRF Yes No | | Date: |

| Document Name | Q\$Noi2879856qqqot012927585 | | |
|----------------------|---|---------------------------|----------------------|
| Туре | Version | Document Identifier | Effective Date |
| eldo chimitrallettoc | 0 0: CURRENT: Most-Recent: Rffgrietiwed | Ი9ᲘᲘ32d58Ი e 4∂¶Რ6 | R1-Jan-2017 14:20:06 |
| Reason For Issue | Auto Issue | | |

| Amendment No. & New Protocol Version No. | Type of Amendment | Reason for Amendment | Other Documents Requiring Amendment | Section(s) Amended | PI Amendment Agreement Signature & Date |
|---|-----------------------|----------------------|-------------------------------------|--------------------|--|
| Amendment No.: | Non-Substantial/Minor | | Informed Consent Yes No | | Signature: |
| Protocol Version No.: | Substantial/ Major | | Safety Statement Yes No CRF Yes No | | Date: |
| Amendment No.: | Non-Substantial/Minor | | Informed Consent Yes No | | Signature: |
| Protocol Version No.: | Substantial/ Major | | Safety Statement Yes No CRF Yes No | | Date: |

| Document Name | @siki2071985tqprot@@7585 | | |
|----------------------|------------------------------------|---------------------|----------------------|
| Туре | Version | Document Identifier | Effective Date |
| eldo chimitrallettoc | 0 0 CURRENT Most-Recent Registived | 090032d580e48566 | R1-Jan-2017 14:20:06 |
| Reason For Issue | Auto Issue | | |

SCHEDULE OF EVENTS

| Study Phase | Screening | | Induction | | | | | | | Rest | Challenge | | | | |
|--|-----------------------------------|------------------|------------------|------------------|------------------|-------------------|-------------------|-------------------|-------------------|--------------------|--------------------|--------------------|--------------------|--------------------|--------------------|
| Study Week | - | Week 1 | | | , | Week 2 Week 3 | | 3 | Week 4-5 | Week 6 | | | | | |
| Procedure/ Assessment | VISIT 1 DAY -14 to DAY 0 | VISIT 2 DAY 1 | VISIT 3 DAY 3 | VISIT 4 DAY 5 | VISIT 5 DAY 8 | VISIT 6 DAY 10 | VISIT 7 DAY 12 | VISIT 8 DAY 15 | VISIT 9 71 YAU | VISIT 10 DAY 19 | VISIT 11 DAY 22 | VISIT 12 DAY 36 | VISIT 13 DAY 38 | VISIT 14 DAY 39 | VISIT 15 DAY 40 |
| Day of Week | - | Mon | Wed | Fri | Mon | Wed | Fri | Mon | Wed | Fri | Mon | Mon | Wed | Thu | Fri |
| Informed Consent | X | | | | | | | | | | | | | | |
| Demographics | X | | | | | | | | | | | | | | |
| Medical History | X | | | | | | | | | | | | | | |
| Current/Concomitant medication review | X | X | X | X | X | X | X | X | X | X | X | X | X | X | X |
| Fitzpatrick Skin Type Assessment | X | | | | | | | | | | | | | | |
| Inclusion/Exclusion Criteria | X | X a | | | | | | | | | | | | | |
| Dermatologist Assessment ^a | X | X | | | | | | | | | | | | | X |
| Subject Eligibility | X | X | | | | | | | | | | | | | |
| Continued Eligibility | | X | X | X | X | X | X | X | X | X | X | X | X | X | X |
| Randomisation | | X | | | | | | | | | | | | | |
| Patch Application ^b | | X | X | X | X | X | X | X | X | X | | X f | | | |
| Patch Removal ^c | | | X | X | X | X | X | X | X | X | X e | | X¹ | | |
| Grading/Assessment of the patch sites ^d | | X g | X | X | X | X | X | X | X | X | X | X ^h | X i | X ^j | X ^j |
| Adverse Events k | | X | X | X | X | X | X | X | X | X | X | X | X | X | X |
| Study Conclusion/Discharge from Study/ | | | | | | | | | | | | | | | X |

| Document Name | ©\$\$\\\\\\\\\\\\\\\\\\\\\\\\\\\\\\\\\\\ | | |
|-----------------------|--|---------------------|----------------------|
| Туре | Version | Document Identifier | Effective Date |
| eldo climitarelleatoc | 0.0; CURRENT; Most-Recent; Revietived | 090032d580e42d66 | 31-Jan-2017 14:20:06 |
| Reason For Issue | Auto Issue | | |

Note: Visit 1 and Visit 2 could occur on the same day but Visit 2 must be within 14 days of Visit 1.

- a. Performed by a qualified dermatologist (Inclusion criteria 3c)
- b. Subjects will report to the study site 10 times during the Induction Phase (9 patch applications). The patches will remain in place for 48 (±2) hours during the week. Patches applied on Friday will remain in place for approximately 72 (±2) hours until Monday.
- c. 30 minutes (up to 1 hour) after each patch removal, a trained blinded assessor will perform an assessment of all test sites for irritation symptoms using the scoring system detailed in Appendix 2.
- d. A trained (by a dermatologist) blinded assessor will perform assessments of all test sites for symptoms of irritation using the scoring system detailed in Appendix 2.
- e. Visit 11 (Day 22) will be the final Induction Phase patch removal and grading/assessment.
- f. Challenge Phase patch application (after 2 week Rest Phase), Visit 12 (Day 36). The challenge patch will be applied to a naïve site and remain in place for 48 (±2) hours.
- g. Visit 2 (Day 1) Baseline assessments of the patch sites will be performed prior to the patch application.
- h. Visit 12 (Day 36) assessments of the naïve challenge patch site will be performed prior to the challenge patch application.
- i. 30 minutes (up to 1 hour) following Challenge patch removal a trained blinded assessor will perform an assessment of the Challenge test site for irritation symptoms using the scoring system detailed in Appendix 2.
- j. Further evaluations of naïve patch removal site will take place 24 (±2) and 48 (±2) hours after patch removal (e.g., apply the patch on Monday, remove the challenge patch on Wednesday, and evaluate the sites on Wednesday, Thursday and Friday).
- k. Subjects are asked to report any adverse events from Visit 2 (or Visit 1 if patch application occurs at Visit 1) and the use of any concomitant medications throughout the study.

| Document Name | GSiki28/7985iqurot2007 585 | | |
|----------------------|---------------------------------------|---------------------|----------------------|
| Туре | Version | Document Identifier | Effective Date |
| eldo climitralleatoc | 0.0; CURRENT; Most-Recent; Registived | 090032d580e4@556 | 31-Jan-2017 14:20:06 |
| Reason For Issue | Auto Issue | | |

PROTOCOL SYNOPSIS FOR STUDY 207585

Brief Summary

A cosmetic product that is freely available to the consumer must be safe when applied under normal or reasonably foreseeable conditions of use. As a general requirement, the safety and compatibility of a new formulation should be confirmed before it is commercialised (Guideline for the Safety Evaluation of Cosmetic Products; Agência Nacional de Vigilância Sanitária, ANVISA, 2012).

Compatibility studies, performed as patch tests, aim to confirm the local tolerance of topical cosmetic products during the first application to the skin, therefore providing assurance that the product is safe for use under maximized conditions (ANVISA, 2012).

The human repeated insult patch test (HRIPT) is a long standing, standard method to determine whether a defined exposure to a product will elicit a dermal irritant or allergic response under exaggerated conditions of exposure. It is also routinely used and accepted as an appropriate methodology to establish the sensitisation potential of topical products (e.g. by the FDA in the U.S.). The HRIPT requires approximately six weeks per a subject and involves three phases: Induction, Rest and Challenge, and is based on the modified Draize test. (Draize, 1944)

In this study the test material and the positive control of saline solution are applied under a semi-occlusive patch to a subject's upper back. The first phase of the study is an Induction Phase; a known amount of product is applied over a defined surface area of skin (amount per unit area) under a semi-occlusive patch. Each patch will remain on the skin for $48 \ (\pm 2)$ hours (weekdays) or $72 \ (\pm 2)$ hours (including inclusive weekends) during this phase. The patch will be removed and the site will be assessed then a new patch will be applied to the same site. After the Induction Phase, subjects will enter a Rest Phase of 2 weeks duration, during which no patches are applied. After the Rest Phase, subjects will return to the clinical site for the Challenge Phase. In this phase a challenge patch of both the test product and control is applied to virgin skin for $48 \ (\pm 2)$ hours then assessed 30 minutes (maximum 1 hour) $24 \ (\pm 2)$ hours and $48 \ (\pm 2)$ hours after patch removal.

The objective of this clinical study is to assess the irritation and sensitisation potential of a cosmetic test product after repeated patch applications to healthy human subjects by following a conventional HRIPT methodology under supervision of a dermatologist.

| Document Name | G\$in:i2:071985t-prot@207 585 | | |
|----------------------|---|---------------------|----------------------|
| Туре | Version | Document Identifier | Effective Date |
| eldo climitralleatbo | 0.0; CURRENT; Most-Recent; Rfferietiwed | 090032d580e4@556 | 31-Jan-2017 14:20:06 |
| Reason For Issue | Auto Issue | | |

Objective(s) and Endpoint(s)

| Objective(s) | Endpoint(s) |
|--|--|
| Primary | |
| To determine the irritation and contact | Trained assessor assessment of local |
| sensitisation potential of a cosmetic facial | tolerance through visual assessment of |
| skin product after repeated patch | cutaneous irritation via the combined |
| applications to the skin of healthy | dermal response and other effects scores |
| subjects. | over the induction and challenge phase. |
| Secondary | |
| To evaluate the general safety of a | Assessment of frequency and severity of |
| cosmetic facial skin product. | Adverse Events |

Study Design

Overall Design

Test site randomized, assessor-blinded, single-center, Human Repeated Insult Patch Test (HRIPT) in healthy subjects to assess the cutaneous irritation and sensitisation potential of a cosmetic facial product, by following a conventional HRIPT methodology under supervision of a dermatologist.

Day -14 to 0 / Visit 1 - Screening Visit

NOTE: Visit 1 and Visit 2 could be combined

The following assessments will be conducted:

- 1. Subject Informed Consent taken
- 2. Subject demographics collected
- 3. Medical history details
- 4. Details of current and concomitant medication collected
- 5. Fitzpatrick Skin Type Assessment (Appendix 3)
- 6. Inclusion/Exclusion criteria
- 7. Dermatologist determination for eligibility to participate in the study (including visual examination of the dorsum scapular region)
- 8. Subject Eligibility

Days 1 to 22 / Visit 2 - Visit 11 - Induction Phase (3 Weeks)

NOTE: Visit 1 and Visit 2 could be combined

The following assessments will be conducted:

- 1. Continued eligibility check
- 2. Current/Concomitant Medications review
- 3. Inclusion/Exclusion criteria review (3c only at Visit 2 if Visit 1 and 2 are not combined).

| Document Name |   | | |
|----------------------|--|------------------|----------------------|
| Туре | Version Document Identifier Effective Date | | |
| eldo climitralleatoc | 0.0; CURRENT; Most-Recent; Rfferietiwed | 090032d580e42556 | 31-Jan-2017 14:20:06 |
| Reason For Issue | Auto Issue | | |

- 4. Dermatologist determination for continued eligibility to participate in the study (Visit 2/Day 1 only if visits not combined).
- 5. Test Site Designation and Randomisation (Visit 2/Day 1 only).
- 6. Baseline grading/assessment of test sites (Visit 2/Day 1 only) as per Appendix 2.
- 7. Patch applications (9 patch applications to the same test site, over 3 consecutive weeks with patches applied on alternate weekdays).
- 8. Patch removal after 48 (\pm 2) hours or 72 (\pm 2) hours over inclusive weekends.
- 9. Reaction grading/assessment performed by a qualified staff member, as per Appendix 2.
- 10. Adverse event assessment

Note: 30 minutes (maximum of 1 hour) after patch removal, sites will be graded/evaluated, then patches will be reapplied to the same sites.

Day 22- Day 36 / Visit 11 – Visit 12 - Rest Phase (2 Weeks)

No Patch Application

Days 36 to 39 / Visit 12 to Visit 14 - Challenge Phase

The following assessments will be conducted:

- 1. Continued eligibility check
- 2. Current/Concomitant Medications review
- 3. Grading/assessment of naïve challenge patch site performed by a qualified staff member. (As per Appendix 2). Prior to Challenge patch application. (Visit 12/Day 36).
- 4. Challenge Phase patch application to naïve site (Visit 12/Day 36).
- 5. Patch removal 48 (\pm 2) or 72 (\pm 2) hours over inclusive weekends after application. (Visit 13/Day 38).
- 6. Reaction grading/assessment performed by a qualified staff member at approximately 30 minutes (maximum 1 hour) after patch removal.
- 7. $24 (\pm 2)$ hours after patch removal (Visit 14/Day 39) subjects will return for assessment performed by a qualified staff member.
- 8. Adverse event assessment.

Day 40 / Visit 15 – End of Study

The following assessments will be conducted:

- 1. Current/Concomitant Medications review
- 2. Adverse event assessment.
- 3. $48 (\pm 2)$ hours after patch removal (Visit 15/Day 40) final challenge patch site assessment performed by a qualified staff member.
- 4. Dermatologist final assessment.
- 5. Subject discharge from the study site following completion of all study

| Document Name | Gsiki207905tqprot20 071585 | | |
|----------------------|---------------------------------------|---------------------|----------------------|
| Туре | Version | Document Identifier | Effective Date |
| eldo climitralleatoc | 0.0; CURRENT; Most-Recent; Registived | 090032d580e42d66 | 31-Jan-2017 14:20:06 |
| Reason For Issue | Auto Issue | | |

procedures.

Type and Planned Number of Subjects

Approximately 280 healthy subjects will be screened to randomize at least 240 subjects to ensure 200 evaluable subjects complete the entire study. If no reaction is observed in 200 subjects, there is a 95% certainty that the actual rate of reaction in the wider population is <1.8%.

Diagnosis and Main Criteria for Inclusion

Healthy male and female volunteers aged 18 to 65 with no dermatological disorders, with a Fitzpatrick skin phototype I to IV will be enrolled into this study.

Product Information

| | Test Product | Reference Product | |
|--------------------------|---|--|--|
| Product Name | Facial micellar cleanser | Saline Solution: Sodium Chloride (NaCl; 0.9%) | |
| Product Formulation | CCI | N/A | |
| Code (MFC) | | Site to supply | |
| Product Format | 200ml clear PET Bottle N/A | | |
| Application Quantity | 0.02 millilitres/square | 0.02 ml/cm^2 | |
| | centimetre (ml/cm ²) | | |
| Route of Administration | Topical dermal application via semi occlusive patch | | |
| Application Instructions | Applied on-site by technician | | |

Statistical Methods

The focus of the statistical analysis will be the evaluation of the frequency and level of irritation and sensitisation responses of the investigational product. All subjects with any product applied will be included in the analysis population.

Individual observations will be assessed based on Appendix 2 and a narrative description of all skin responses, both in the induction and challenge phases, will be provided. A frequency tabulation of the number of subjects with any skin response versus those without any skin response will be presented by treatment group for both the induction and challenge phases of the study. If there are subjects with non-zero dermal response or superficial irritation scores, a combined dermal and others effects

| Document Name |   | | |
|----------------------|---|---------------------|----------------------|
| Туре | Version | Document Identifier | Effective Date |
| eldo climitralleatoc | 0.0; CURRENT; Most-Recent; Rfferietiwed | 090032d580e42566 | 31-Jan-2017 14:20:06 |
| Reason For Issue | Auto Issue | | |

score will be determined across all time points over the induction and challenges phases as well as at each assessment time point and summarised using descriptive statistics.

No interim or subgroup analyses are planned.

Adverse Events (AE) will be tabulated according to the current version of the Medical Dictionary for Regulatory Activities (MedDRA). Frequencies and percentages will be presented overall, for each system organ class, and for each preferred term. Summaries of treatment-emergent AEs, treatment-related AEs, AEs leading to discontinuation, and serious AEs will be completed. For treatment-related AEs, these will also be presented by treatment/test site.

Detailed methodology for summary and statistical analyses of the data collected in this study will be documented in a Statistical Analysis Plan, which will be maintained and signed off prior to study unblinding.

| Document Name | G\$in:i2:071985t-prot@207 585 | | |
|----------------------|---|---------------------|----------------------|
| Туре | Version | Document Identifier | Effective Date |
| eldo climitralleatbo | 0.0; CURRENT; Most-Recent; Rfferietiwed | 090032d580e4@556 | 31-Jan-2017 14:20:06 |
| Reason For Issue | Auto Issue | | |

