Any skin response at a patched site will be clinically assessed using the criteria recommended by the US Department of health and Human Services Food and Drug Administration (FDA), 1999.

Each of the scores represents an effect that is localised in a representative portion of the patch area, defined as 25% or more of the patch test site. Individual observations will be recorded in tables and a narrative description of all skin responses (any

| Document Name | Gsikni2θ/1965t-prot/207 1585 | | | |
|----------------------|---------------------------------------|---------------------|----------------------|--|
| Туре | Version | Document Identifier | Effective Date | |
| eldo climitralleatoc | 0.0; CURRENT; Most-Recent; Registived | 090032d580e42556 | 31-Jan-2017 14:20:06 | |
| Reason For Issue | Auto Issue | | | |

score>0) will be provided. Superficial irritation scores are only provided if there is a dermal response score >0.

Each Superficial Irritation Score should be reported as a letter. The combined score will equal the sum of the dermal response score plus the numerical equivalent of the superficial irritation score (e.g. dermal response score=3 and superficial irritation score=" $^{\circ}$ C" implies a combined score of 3 + 2 = 5).

If a subject develops a combined score of 3 or greater at any point during the Induction phase, the patch will be applied to an adjacent naïve site for the next application. If a combined score of 3 or greater occurs at the naïve site, no further patch applications will be made. Such reactive subjects will however, receive patches on naïve test sites during the challenge phase of the study unless, in the opinion of the Investigator, it would be unwise to do so.

Dermal irritation or sensitisation reactions within the patch area (i.e., irritation reactions outlined in Appendix 2) will not be recorded as AEs during the study. Reactions to the patch itself will also not be recorded as AEs. Unexpected reactions (e.g., rash, hives) will be recorded as AEs. These responses are expected in these study conditions and will be disregarded in evaluations, using the negative control (saline solution) as the standard for determining the expected degree of reaction.

Application Amount Justification:

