5.3. Product Assignment

Each subject will have the test product and the negative control applied to their backs (dorsum region). The location for each study product application for each subject will be assigned in accordance with the randomisation schedule generated by the Biostatistics Department, GSKCH, prior to the start of the study, using validated internal software.

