6.2.1 Application of patches

The test product and saline solution (0.02 ml/cm² of each product) will be applied to a paper disc (or cell) contained within an adhesive patch. The number of cells available on the patch test tape can vary but in this study one will be used for test product and one for the reference; saline solution). The patch is then applied onto the dorsum (scapula region) of each subject for a period of 48 ± 2 hours, the sequence of the product application to the cells will be randomly assigned to each subject according to the randomisation schedule.

Induction Phase:

Visit 2/Day 1 of the induction phase could be combined with Visit 1.

On Day 1 of the Induction Phase, eligible subjects will return to the study site and another dermatological assessment will be conducted to ensure subject continued eligibility (if Visits 1 and 2 are not combined), as well as a review of concomitant medications since screening. The test site will be designated above the waist between the left scapula and waistline and away from the spinal mid-line. The site of application of the products will then be randomly assigned. Baseline grading/assessment of the test sites will then be performed.

There will be 9 patch applications to the same test site of both the test product and saline solution over 3 consecutive weeks during the induction phase, with a patch applied on alternate weekdays each week (Monday, Wednesday, and Friday). Each patch will remain in place for 48 ± 2 hours on weekdays and 72 ± 2 hours on weekends. The patch will be removed and the treated areas will be cleaned with saline solution. After 30 minutes (maximum of 1 hour) the site will be graded/evaluated as per the scale in Appendix 2. A new patch will then be reapplied to the same site.

| Document Name | G\$in:i2:071985t-prot@207 585 | | |
|----------------------|---|---------------------|----------------------|
| Туре | Version | Document Identifier | Effective Date |
| eldo climitralleatoc | 0.0; CURRENT; Most-Recent; Rfferietiwed | 090032d580e42556 | 31-Jan-2017 14:20:06 |
| Reason For Issue | Auto Issue | | |

Rest Phase:

After the last patch removal and grading/evaluation of the Induction Phase, subjects will enter a Rest Phase of 2 weeks. During this time there will be no product patch applications.

Challenge Phase:

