9.3.2. Primary Analysis(es)

The primary analysis will be based on the irritation (dermal response) and superficial irritation (other effects) scores/grades assessed using the scales described in Tables 1 and 2 of Appendix 2. Individual observations will be assessed based on these scales and a narrative description of all skin responses, both in the induction and challenge phases, will be provided.

No formal statistical inference will be performed.

The number and percentage of subjects recording each category of score/grade, as well as any skin response versus those without any skin response will be presented by treatment group at each assessment time point and over the induction and challenge phases using the maximum grade/score. If there are subjects with non-zero dermal response or other effects scores, then the dermal response, other effects and a combined dermal and others effects score will be summarised using descriptive statistics at each assessment time point and over the induction and challenges phases using a total score across time points.

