5.1 Templates for the Tables, Listings and Figures.....15

Document Name	gsk-207585-reporting-and-analysis-plan		
Type	Version	Document Identifier	Effective Date
eldo_controlled	0.1; CURRENT; Most-Recent; Reviewed	090032d580e125d0	
Reason For Issue			

The purpose of this Statistical Analysis Plan is to describe the planned analyses and output to be included in the Clinical Study Report for Protocol 207585. The SAP will be finalized prior to data base freeze and treatment code un-blinding.

1 Study details

The purpose of this trial is to assess the cutaneous irritation and sensitisation potential of a cosmetic facial product by following a conventional Human Repeated Insult Patch Test (HRIPT) methodology under supervision of a dermatologist.

General safety and tolerability will be assessed based on the frequency and severity of Adverse Events (AEs).

This is a single-center, randomised, assessor blind study in healthy subjects aged 18-65 years, with a Fitzpatrick skin type phototype of I to IV. Subjects will be exposed to repeated insult dermal semi-occlusive patch applications of a cosmetic facial skin product and negative control (saline solution).

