2.4 Analysis of Dermal Responses

2.4.1 Primary endpoint

2.4.1.1 Primary endpoint definition

The primary analysis will be conducted to assess the cutaneous irritation and sensitisation potential of the test and control product, based on the combined irritation (dermal response) and superficial irritation (other effects) score/grade after patch removal during the induction and challenge phases using the ITT population.

Calculation of combined score (dermal response and superficial irritation):

Document Name	gsk-207585-reporting-and-analysis-plan		
Type	Version	Document Identifier	Effective Date
eldo_controlled	0.1; CURRENT; Most-Recent; Reviewed	090032d580e125d0	
Reason For Issue			

GSK Consumer Healthcare

Confidential

Page 10

Statistical Analysis Plan

207585

The combined score for dermal response and superficial irritation (other effects) will be calculated in the following way –

Combined score = dermal response score + numerical equivalent of the superficial irritation score

Where, the dermal response scale is described in the Table 2 below, and the superficial irritation scores in Table 3 below.

Table 2: Skin Irritation Scoring System (Dermal Response)

CII

Table 3: Superficial Irritation Score System (Symbols and numerical Equivalents)

CII

* The letter grades assigned to the irritation responses will be converted to scores for the statistical analysis process. Grading will be conducted throughout the trial by a qualified staff member.

For example, if the dermal responses score=3 and superficial irritation letter ="C" then the combined score will be:

Combined score = 3 + 2 = 5

 GlaxoSmithKline	Document Name	gsk-207585-reporting-and-analysis-plan		
	Type	Version	Document Identifier	Effective Date
	eldo_controlled	0.1; CURRENT; Most-Recent; Reviewed	090032d580e125d0	
	Reason For Issue			

GSK Consumer Healthcare

Confidential

Page 11

Statistical Analysis Plan

207585

Only subjects with at least one combined score > 0 at any visit will be summarised. The frequency of scores will be summarized in each category of combined score by treatment group and at each time point for both induction and challenge phases. The maximum combined score irrespective of visits for each phase will also be presented ([Table 14.2.1.1](#)). No formal statistical inference will be performed.

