4.1 List of Tables, Listings and Figures

4.2 Tables

Table Number	Table Title (Population)	Template
14.1.1	Subject Disposition (All Screened Subjects)	Appendix 2
14.1.2.1	Subject Demographics and Baseline Characteristics (Safety Population)	Appendix 2
14.1.2.2	Subject Demographics and Baseline Characteristics (ITT Population)	14.1.2.1
14.2.1.1	Frequency of Combined Score by Phase, Visit and Treatment and Maximum Combined Score (ITT Population)	Appendix 2
14.2.2.1	Frequency of Dermal Response Score by Phase, Visit and Treatment and Maximum Dermal Response Score (ITT Population)	Appendix 2
14.2.2.2	Frequency of Superficial Irritation (other effects) Score by Phase, Visit and Treatment and Maximum Superficial Irritation (other effects) Score (ITT Population)	Appendix 2
14.3.1.1	Treatment emergent Adverse Event (Safety Population)	Appendix 2
14.3.1.2	Treatment emergent Adverse Event by Severity (Safety Population)	Appendix 2
14.3.1.3	Treatment emergent Treatment Related Adverse Event (Safety Population)	14.3.1.1
14.3.1.4	Treatment emergent Treatment Related Adverse Event by Severity (Safety Population)	14.3.1.2

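### No planned summary table links a subject's cleanser and saline sites, although the design pairs them; a descriptive within-subject table would add this at almost no cost

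*Protocol*

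**What the plan says.** The design is within-subject. Protocol 5.3 states: "Each subject will have the test product and the negative control applied to their backs (dorsum region"). Protocol 6.2.1 adds that "in this study one will be used for test product and one for the reference; saline solution", with the position of the two products randomised for each subject. Protocol 3.4 (Patch Assessments) says that expected reactions are set aside in evaluations, "using the negative control (saline solution) as the standard for determining the expected degree of reaction".

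The planned summaries are by product:

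- The Synopsis (Statistical Methods) says "A frequency tabulation of the number of subjects with any skin response versus those without any skin response will be presented by treatment group". This applies to each of the two phases. Protocol 9.3.2 repeats this for each score category and for the phase maximum.
- SAP 2.4.1.1 says "The frequency of scores will be summarized in each category of combined score by treatment group and at each time point", plus the maximum per phase. The primary table, 14.2.1.1, has one cleanser column and one saline column. Tables 14.2.2.1 and 14.2.2.2 have the same layout.
- SAP 2.4.1.2 (hypothesis, model and method) and 2.4.1.3 (supportive analyses) are marked as not applicable. Protocol 9.3.2 states: "No formal statistical inference will be performed".

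The protocol also promises subject-level material. Section 3.4 and Appendix 2 plan to present each individual's responses to product and saline at each time point, with a narrative for every score above zero. The SAP says it will "describe the planned analyses and output to be included in the Clinical Study Report for Protocol 207585". Its listings (section 4.3) cover deaths, serious events, randomisation, protocol violations and adverse events. Neither individual skin scores nor narratives appear there.

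**The concern.** Some redness from tape and covering can be expected at either cell. The informative quantity for irritation is therefore what happens at the cleanser cell beyond what happens at the same person's saline cell. Two separate columns do not carry that information. The same pair of percentages can arise when every saline responder also responds to cleanser and a further group responds to cleanser alone. It can also arise when the two sets of responders are different people. The first pattern is a consistent excess and the second looks more like scattered background. A reader who compares the columns has no interval for the difference, and any interval built from the columns alone would have to ignore the pairing.

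The point concerns the irritation half of the primary objective, in the induction phase. It does not concern the reading of the challenge phase for sensitisation.

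**Working it through.** **The plan's own figure.** Protocol 9.1 gives an upper bound of 1.8% if none of 200 subjects reacts. The two-sided 95% exact limit is 1 − 0.025^(1/200) = 1.83%, which agrees. (The one-sided limit would be 1 − 0.05^(1/200) = 1.49%.) This is a one-sample bound for the zero-reaction case. It does not involve saline and is unaffected by the point made here.

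**Inputs for the illustration.** n = 240 is the planned number randomised (Protocol 9.1), taken here as all having scores at both sites. The documents give no response rates, so 20 cleanser responders and 12 saline responders are assumptions.

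**Notation.** Let a = subjects responding at both sites, b = cleanser only, c = saline only. Then a + b = 20 and a + c = 12.

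**What the planned columns show.** 20/240 = 8.3% and 12/240 = 5.0%. The difference is (b − c)/n = 8/240 = 3.33 points whatever the overlap a. Since a can be anything from 0 to 12, b can be anything from 20 down to 8.

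**What they do not show.** The paired standard error is SE = √[b + c − (b − c)²/n] / n, and the interval is 3.33 ± 1.96 × SE.

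| Overlap a | Cleanser only b | Saline only c | SE (points) | 95% CI (points) |
|---|---|---|---|---|
| 12 (full) | 8 | 0 | √(8 − 64/240)/240 = 1.16 | 1.06 to 5.60 |
| 6 | 14 | 6 | √(20 − 64/240)/240 = 1.85 | −0.29 to 6.96 |
| 0 (none) | 20 | 12 | √(32 − 64/240)/240 = 2.35 | −1.27 to 7.93 |

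**Unpaired reading of the same margins.** √[0.0833 × 0.9167/240 + 0.05 × 0.95/240] = 2.27 points. If the two sites responded independently, the expected overlap would be 20 × 12/240 = 1 subject. That gives b = 19, c = 11 and SE = √(30 − 64/240)/240 = 2.27, the same value. With more overlap than chance, the unpaired figure is too wide; with less, it is slightly too narrow.

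**Check with other assumptions.** With 200 subjects and Newcombe's interval for paired proportions:

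| Cleanser v saline responders of 200 | Difference (points) | 95% CI, full overlap | 95% CI, no overlap |
|---|---|---|---|
| 10 v 4 | 3.0 | 0.4 to 6.5 | −0.8 to 7.2 |
| 20 v 12 | 4.0 | 1.1 to 7.6 | −1.6 to 9.7 |
| 30 v 20 | 5.0 | 1.8 to 8.7 | −2.0 to 12.0 |

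In each row the planned columns are identical for the two overlap cases.

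**The case against.** The strongest reply is that the study is descriptive and centred on one product. The objective and endpoint concern the cosmetic product's own scores, the sample size is a one-sample zero-event bound, and no contrast with saline is specified. The sentence naming saline as the standard closes a paragraph about which reactions are recorded as adverse events; neither Protocol 9.3.2 nor SAP 2.4.1.1 repeats it. This stands to the extent that no promised paired analysis is missing. It does not remove the value of a descriptive cross-table: the control is on the same back, and Protocol 9.2.3 and SAP 2.4.1.1 both bring the control product into the primary evaluation.

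Three stronger readings are tempting, and the documents do not support them.

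- *A reader might infer that no planned output links the two sites.* The individual responses and narratives promised in the protocol would do so. What remains is that the cleanser-only count would have to be made by hand, with no interval, and that the SAP output list does not include this material.
- *A reader might infer that the excess over saline is hidden.* The net excess is visible, because the point difference is the same paired or unpaired.
- *A reader might infer that the plan analyses paired data as two independent groups.* It plans no comparison and no standard error, so it makes no such error.

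It is also fair that zero overlap is less than chance would give, and that adjacent cells on one back more plausibly respond together. The range from 1.16 to 2.35 is a span between extremes, not a forecast.

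**Conclusion.** The point holds as an improvement to the summaries, not as a mistake in the plan. No planned summary table cross-classifies a subject's two sites, so neither the number reacting to cleanser only nor the precision of the paired difference can be read from the tables. Under the assumed margins of 20 and 12 among 240, the cleanser-only count could be anywhere from 8 to 20 and the standard error anywhere from 1.16 to 2.35 points. The real size depends on response rates and overlap that the documents do not state. If no reactions occur, which is the case the sample-size statement addresses, the effect is nil.

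**What to change.** In SAP 2.4.1.1 and Table 14.2.1.1, add one block for the induction phase containing:

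1. a within-subject 2x2 table of cleanser combined score above zero (yes/no) by saline combined score above zero (yes/no);
2. the distribution of cleanser maximum minus saline maximum;
3. the paired difference in proportions with a descriptive 95% confidence interval.

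Two definitions must be written with it.

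- **Reading window.** Take each site's maximum over the post-application induction readings at Visits 3 to 11. The existing template defines induction as Visits 2 to 10, which includes the pre-patch baseline at Visit 2 and places Visit 11 in the rest phase. The Schedule of Events identifies Visit 11 as the final induction removal and grading.
- **Denominator.** Use ITT subjects with post-application scores at both sites, and state the number. The ITT definition admits subjects with scores from only one site, who cannot enter a paired table.

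No hypothesis test is needed, so the statement that no formal inference will be performed can stay. The cost is one table block and a short addition to the SAP text, with no new data, visits or subjects. The SAP is to be finalised before unblinding, so the block can be specified before results are known.
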